17.4.1. Importance rating. 1,2,3,4,5

17.5. Is the treating team involved in the decision for terminal sedation? Yes, No, Don't know, NA

17.5.1. Importance rating. 1,2,3,4,5

17.6. Is the patient involved in the decision for terminal sedation? (if feasible)?

Yes, No, Don't know, NA

17.6.1. Importance rating. 1,2,3,4,5

17.7. Is the family involved in the decision for terminal sedation? Yes, No, Don't know, NA

17.7.1. Importance rating. 1,2,3,4,5**17.8. Comments (free text)****18. Withholding of treatment (i.e. avoiding escalation of an already administered treatment or avoiding to add a new treatment)**

18.1. Is it legally allowed in your country? Yes, No, Don't know, Not applicable (NA) *(if no/Don't know/NA – move on to question 19.1.)*

18.2. Do you feel comfortable with existing legislation? Yes, No, Don't know, Not applicable (NA)

18.2.1. Importance rating. 1,2,3,4,5

18.3. Do you feel empowered to apply it? Yes, No, Don't know, NA

18.3.1. Importance rating. 1,2,3,4,5

18.4. Do you feel empowered to document it? Yes, No, Don't know, NA

18.4.1. Importance rating. 1,2,3,4,5

18.5. Does it include feeding? Yes, No, Don't know, NA

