The final version of the questionnaire is presented in the Appendix of the current protocol. The questionnaire was developed based on published, relevant literature (16-23), investigator consensus and comments collected by preliminary testing; the latter comprised administration of the questionnaire to a total of 30 Danish, British and Greek ICU clinicians (10 from each country). Danish and British clinicians were asked to qualitatively assess the readability and understandability of the survey questions and provide comments for improvement as regards content and clarity. Greek clinicians were asked to first respond to the questionnaire, in order to obtain an estimate of the actual time required for survey completion, and subsequently also provide their comments on content and clarity.

In its finalized form, the survey consists of an introduction and 4 sections. The introduction includes core definitions concerning advance directives and shared decision making (16), palliative care (<https://www.who.int/europe/news-room/fact-sheets/item/palliative-care>), treatment limitation (17), active shortening of the dying process (or euthanasia) (17), and family (18). The first section aims at collecting data on participant characteristics, including age, gender, religion, location of professional activity (including hospital name), professional focus, grade and experience. The second section includes questions on patient-level, family-level and healthcare-level domains of palliative care (19-21), as well as participant-rating (5-point scale) of the importance of domain elements; these elements pertain to physical and psychosocial aspects of care, communication, family support and system-level support (19-21). The third section includes questions (and rating by 5-point scale wherever appropriate) about EOL legislation and practices such as and applicability of and clinician-compliance with advance directives, treatment limitation (i.e. withholding or withdrawing of life-sustaining treatments), euthanasia, terminal analgesia/sedation, EOL decision-making and family presence during cardiopulmonary resuscitation (17, 21). Lastly, the fourth section includes 12 questions with two-choice answers (i.e. yes/no) in the context of a recently introduced EOL practice score (17, 22) (with definitions of score subcomponents appended), and an additional 3 general questions about palliative care practice in the participant's ICU.

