Internet protocol (IP) address data will be used to ensure the uniqueness of survey participants. More specifically, unlimited, repetitive access to the questionnaire will be allowed from an IP address of a client computer until survey submission. However, following submission of the filled questionnaire through an IP address, will result in discontinuation of survey accessibility through that particular IP address.

Due to the use of snowballing dissemination and sharing of invitation links, it will not be possible to calculate the survey response rate. However, survey completion rate will actually be calculated by dividing the total number of submitted questionnaires to the number of first-survey page visitors. Furthermore, questionnaire completeness rate will be calculated by dividing the number of questionnaires without any missing response to the total number of submitted questionnaires. Missing responses will correspond to questions to which participants will have indicated that they do not wish to answer (see also above). Mutually contradictory responses from participants originating from the same study center, or the same city, or the same country constitute a possibility, especially for the third and fourth section of the survey (15, 17, 22-24). For example, two or more

participants from the same center/city/country may respond differently as regards the legal bindingness of advance directives. In such cases, mutually contradictory responses will be used to estimate the extent of country-specific variation in the perception of law and/or local palliative care practice.

Study outcomes

The primary outcomes will be the absolute numbers of positive (i.e. yes) responses to question groups 10 through 14 of survey section 2, 15 through 23 of section 3, and 24 and 25 of section 4.

Secondary outcomes will include 1) the absolute numbers of positive (i.e. yes) responses to question groups 10 through 14 of section 2 in the presence vs. absence of a positive response to question 24.12 of section 4.

Statistical analysis plan

Statistical analyses will include 1) descriptive statistics; 2) assessment of distribution normality (by Kolmogorov Smirnov test); 3) assessment of European country-/region-level heterogeneity in the responses; and 4) region-level comparisons of responses (17).

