We expect to determine substantial heterogeneity in the responses, primarily between northern and southern Europe and central and southern Europe, and generally between countries with high vs low palliative care service integration.

High palliative care score will be defined as presence of at least 16 positive responses (out of 24 possible positive responses) to question groups 10 through 14 of survey section 2.

Generalized estimating equations (GEE) models with robust SEs and exchangeable working correlation structure accounting for the factor center (24) will be applied to examine associations between a high palliative care score, the 9 clinician demographic variables of survey section 1 [with "country" stratified according to "northern, central or southern European region" (17,23,24)], and the EOL practice score and/or its subcomponent EOL practice variables listed in question group 24 of survey section 4. The dependent variable in this analysis will be high palliative care score, yes or no. Reference category for region will be "southern Europe" (17). The maximum number of GEE explanatory variables will be 21. Consequently, our target sample size of 500 participants is expected to result in approximately 24 observations (i.e. response data-points) per variable; this exceeds the recommended threshold of 20 observations per variable (17,23,24,25) by 20% and establishes an adequate safety margin, aimed at addressing the possibility of missing responses.

Significance will be set at two-sided $P < 0.05$. Analyses will be conducted using the latest versions of SSPS or R software.

Expected general benefits from the current study

Survey results will likely serve to refine the EPIC harmonized practice model of palliative care, further clarifying the concepts of primary versus specialist palliative care and ICU clinicians' role in the practice concept. Results from the survey on legal issues are expected to inform stakeholders involved in policy and legislation, and improve security for ICU clinicians in the respective countries and Europewide.

Expected benefits for the conduct of the EPIC trial

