14.5.1. If yes, please specify who?

14.5.2. Importance rating. 1,2,3,4,5

14.6. Comments (free text)

Perceptions about legal framework for end of life/ treatment limitation decisions

Please use the following 5-point scale to rate the importance of the following elements of treatment limitation decisions; please note that "your country" = "the country in which you work"

- 1=unimportant
- 2=low importance
- 3=average importance
- 4=high importance
- 5=maximum importance

At the end of each domain, it is possible to clarify your responses and/or add other comments

15. Regarding Do-not-attempt cardiopulmonary resuscitation (DNACPR) orders

15.1. Are they legally allowed in your country? Yes, No, Don't know (*if no/Don't know – move on to question 16.1.*)

15.2. Do you feel comfortable with existing legislation? Yes, No, Don't know, Not applicable (NA)

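### The importance ratings after the four feeding and hydration questions (18.5, 18.6, 19.5, 19.6) state neither what is rated nor in which direction, so their summaries cannot be interpreted

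*Combined protocol and SAP*

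**What the plan says.** The protocol (Development and testing of the questionnaire) describes section 2 as including "participant-rating (5-point scale) of the importance of domain elements", and says that section 3 uses a 5-point rating wherever appropriate.

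In the Appendix the two sections introduce the scale differently:

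- **Section 2 (provision of care).** The instruction says what importance means: the value that the clinician attaches to an aspect of care for ICU patients near death whose poor prognosis is on record.
- **Section 3 (legal framework).** The instruction asks respondents to "rate the importance of the following elements of treatment limitation decisions", labels the five points, and explains that the country meant is the one where the respondent works. It does not define importance.

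Question group 18 (withholding) then asks "18.5. Does it include feeding? Yes, No, Don't know, NA" and puts an unlabelled rating, 18.5.1, beneath it. Hydration follows at 18.6, and group 19 (withdrawing) repeats the pair at 19.5 and 19.6. Free-text comment fields close the groups at 18.7 and 19.7.

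On analysis, Study outcomes states "The primary outcomes will be the absolute numbers of positive (i.e. yes) responses to question groups 10 through 14", with the further groups listed after it. The statistical analysis plan adds descriptive statistics, "3) assessment of European country-/region-level heterogeneity in the responses", and comparisons between regions.

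**The concern.** A rating can be read only if the respondent and the analyst agree on what is being rated. Questions 18.5, 18.6, 19.5 and 19.6 are factual: they ask what withholding or withdrawing covers. They describe no practice that could itself be more or less important. Someone who answers No and marks 5 may think that the exclusion matters and should stay, or that inclusion matters and is missing. A third person may mean only that the matter should be settled clearly.

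One of the survey's two main questions is how clinicians perceive the medico-legal framework. Whether treatment limitation extends to feeding and hydration belongs to that question. If these ratings are tabulated by country or region, a reader will naturally take a high value as support for one side, and the data cannot show which.

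**Working it through.** **1. Check the item count against the plan's own figure.** Yes/No items in groups 10 to 14: 6 + 3 + 6 + 4 + 5 = 24. This agrees with the plan's score definition, "at least 16 positive responses (out of 24 possible positive responses) to question groups 10 through 14".

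**2. Count the ratings.**

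- Section 2: one for each item, 24.
- Section 3, groups 15 to 23: 7 + 4 + 6 + 5 + 5 + 4 + 4 + 4 + 2 = 41, against 49 Yes/No items.
- Total: 24 + 41 = 65.

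**3. Sort the 41 section 3 ratings by what they follow.**

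| Type of question | Items | Ratings |
|---|---|---|
| Includes feeding or hydration | 18.5, 18.6, 19.5, 19.6 | 4 |
| Comfort with existing legislation | 15.2, 16.3, 17.2, 18.2, 19.2, 20.2, 21.2 | 7 |
| Empowered to apply or document | two in each of groups 15 to 21 | 14 |
| Involvement, shared decisions, family presence | 15.5-15.8, 17.5-17.7, 20.5, 21.5, groups 22 and 23 | 15 |
| Regular review of advance directives | 16.6 | 1 |
| Total | | 41 |

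The direction problem affects 4/65 = 6.2% of all ratings, or 4/41 = 9.8% of those in section 3. With the seven comfort items it is 11/41 = 26.8% of section 3, which leaves 30.

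**4. What the data can and cannot identify.** Take respondents who answered No to 18.5. Let p be the proportion of them who rate 4 or 5, and let a be the proportion who rate 4 or 5 because they think feeding should be included. The answers give p and nothing more about a than 0 ≤ a ≤ p.

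For two regions with p₁ and p₂, the difference a₁ − a₂ can lie anywhere from −p₂ to +p₁. Once both proportions exceed zero, even its sign is undetermined. A larger sample does not narrow this range. The same argument, reversed, applies to those who answered Yes.

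**5. Compare a section 2 item.** At 10.1 the text states a practice (daily pain assessment), asks whether it is routine, and rates it under a stated definition. A 5 after No has one natural reading: valued but not routine. Question 18.5 offers neither a stated practice nor a definition.

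**6. Check whether a named analysis depends on these ratings.** The primary outcomes count Yes answers, and so does the secondary one ("Secondary outcomes will include 1) the absolute numbers of positive (i.e. yes) responses to question groups 10 through 14", split by answer to 24.12). The score counts Yes answers. For the model, "The maximum number of GEE explanatory variables will be 21", and 9 demographic variables + 12 end-of-life practice variables = 21, so no rating is among them. The four ratings could enter only through the general descriptive and regional analyses of responses.

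**The case against.** The strongest reply is that the defect is small and partly guarded against. The instruction does give a general object, respondents may clarify their answers at the end of each domain, and 30 clinicians tested the questionnaire, with comments sought on content and clarity. All of that is true. But the comment fields help only for respondents who use them, and the final wording still leaves the object unnamed at these lines.

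A reader might infer three stronger points. The documents do not support them.

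- **That section 3 ratings in general do not say what is rated.** For the 15 items on involvement, shared decisions and family presence, the object can reasonably be inferred from the question. The empowerment items are closer to the comfort items, and where to draw that line is a judgement. Only the four feeding and hydration ratings allow opposite meanings for the same score.
- **That a No can never be split into not valued and valued but not done.** In groups 10 to 13 all 6 + 3 + 6 + 4 = 19 practice answers are paired with a rating under a stated definition. The split is possible there; the plan simply does not specify it.
- **That the ratings will be discarded.** They are 65 of the 151 closed answers in sections 2 to 4 (24 + 49 + 12 + 1 = 86 other closed answers; 65/151 = 43.0%), and none enters a named outcome. But the planned descriptive and regional analyses refer to responses without restriction and may include them. The 43% is therefore not a measure of lost data.

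**Conclusion.** The point holds as a narrow measurement defect. Four of 65 importance ratings cannot be interpreted in direction under the present wording, and seven more are mildly ambiguous between the law and the respondent's comfort with it. The Yes-count outcomes, the high palliative care score and the regression model are unaffected. The defect deserves correction because analysis cannot repair it afterwards. The conclusion assumes that the electronic form shows the rating lines as the Appendix prints them, with no further label. It needs no assumption about response frequencies. The matter is minor.

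**What to change.** Before launch, name the rated object at the 11 lines. For the four feeding and hydration ratings, for example: *How important is it that the law states whether feeding may be withheld?*, adapted for hydration and for withdrawing. For the seven comfort ratings: *How important is clear legislation on this practice?* A general definition of importance at the head of section 3 would help but would not be enough, because the direction has to be fixed item by item.

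If responses were already collected with the present wording (collection is planned for January to July 2024), do not reword midway, since that would split the data. Report the four ratings as not interpretable in direction, and draw no regional conclusion from them.

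The cost is 11 lightly reworded lines that the 30-clinician pretest did not cover.

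Optionally, for the 19 items in groups 10 to 13, report by region the percentage of respondents with practice No and importance 4 or 5, with intervals that allow for clustering by centre. With three regions that is 19 × 3 = 57 descriptive estimates. This would be an extra use of data already collected, not the correction of an error.

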18.5.1. Importance rating. 1,2,3,4,5

18.6. Does it include hydration? Yes, No, Don't know, NA

18.6.1. Importance rating. 1,2,3,4,5**18.7. Comments (free text)****19. Withdrawing of treatment (i.e. stopping/removing an already prescribed/ongoing treatment)**

19.1. Is it legally allowed in your country? Yes, No, Don't know, Not applicable (NA)

(if no/Don't know/NA – move on to question 20.1.)

19.2. Do you feel comfortable with existing legislation? Yes, No, Don't know, Not applicable (NA)

19.2.1. Importance rating. 1,2,3,4,5

19.3. Do you feel empowered to apply it? Yes, No, Don't know, NA

19.3.1. Importance rating. 1,2,3,4,5

19.4. Do you feel empowered to document it? Yes, No, Don't know, NA

19.4.1. Importance rating. 1,2,3,4,5

19.5. Does it include feeding? Yes, No, Don't know, NA

19.5.1. Importance rating. 1,2,3,4,5

19.6. Does it include hydration? Yes, No, Don't know, NA

19.6.1. Importance rating. 1,2,3,4,5

19.7. Comments (free text)

20. Euthanasia in adults

20.1. Is it legally allowed in your country? Yes, No, Don't know, Not applicable (NA)
(if no/Don't know/NA – move on to question 22.1.)

20.2. Do you feel comfortable with existing legislation? Yes, No, Don't know, Not applicable (NA)

20.2.1. Importance rating. 1,2,3,4,5

20.3. Do you feel empowered to apply it? Yes, No, Don't know, NA

20.3.1. Importance rating. 1,2,3,4,5

20.4. Do you feel empowered to document it? Yes, No, Don't know, NA

20.4.1. Importance rating. 1,2,3,4,5

20.5. Is the treating team involved in the euthanasia decisions?

Yes, No, Don't know, NA

20.5.1. Importance rating. 1,2,3,4,5

20.6. Comments (free text)

21. Euthanasia in children

21.1. Is it legally allowed in your country? Yes, No, Don't know, Not applicable (NA)

(if no/Don't know/NA – move on to question 22.1.)

21.2. Do you feel comfortable with existing legislation? Yes, No, Don't know, Not applicable (NA)

21.2.1. Importance rating. 1,2,3,4,5

21.3. Do you feel empowered to apply it? Yes, No, Don't know, NA

21.3.1. Importance rating. 1,2,3,4,5

21.4. Do you feel empowered to document it? Yes, No, Don't know, NA

21.4.1. Importance rating. 1,2,3,4,5

21.5. Is the treating team involved in the euthanasia decisions?

Yes, No, Don't know, NA

21.5.1. Importance rating. 1,2,3,4,5

21.6. Comments (free text)

22. Regarding EoL decisions

22.1. Do families participate in EoL decisions (adults)? Yes, No, Don't know

22.1. Importance rating. 1,2,3,4,5

22.2. Do families participate in EoL decisions (children)? Yes, No, Don't know

22.2.1. Importance rating. 1,2,3,4,5

22.3. For adults: Are EoL decisions reached through shared decision making? Yes, No, Don't know

22.3.1. Importance rating. 1,2,3,4,5

22.4. For children: Are EoL decisions reached through shared decision making?

Yes, No, Don't know

22.4.1. Importance rating. 1,2,3,4,5

22.5. Comments (free text)

23. Family presence during Cardiopulmonary resuscitation (CPR)

23.1. For adults: is family presence allowed during CPR? Yes, No, Don't know

23.1.1. Importance rating. 1,2,3,4,5

23.2. For children: is family presence allowed during CPR? Yes, No, Don't know

23.2.1. Importance rating. 1,2,3,4,5

23.3. Comments (free text)

24. In your daily practice in ICU, do you have:**24.1. Intensive care unit (ICU) routine family meetings?** Yes, No**24.2. ICU daily deliberation for appropriate level of ICU care?** Yes, No**24.3. ICU end-of-life discussions during weekly meetings?** Yes, No**24.4. ICU written triggers for limitations?** Yes, No**24.5. ICU written end-of-life guidelines?** Yes, No**24.6. ICU end-of-life protocols?** Yes, No**24.7. ICU palliative care specialty consultations?** Yes, No**24.8. ICU ethics consultations?** Yes, No**24.9. ICU staff taking communication courses?** Yes, No**24.10. ICU staff taking Bioethics Courses?** Yes, No**24.11. Country end-of-life guidelines?** Yes, No**24.12. Country end-of-life legislation?** Yes, No**24.13. Any additional comments (free text)**

EOL Practice Variable	Definition
Routine family meetings	Regular (i.e. on admission and at least twice a week) scheduled conferences of at least one member of an ICU patient's family and at least one member of the treating team aimed at a) determining/clarifying the patient's health status, and comorbidities, b) patient values, preferences, and goals concerning treatment options; and c) conveying honest, accurate, and evidence-based information about patient clinical status and current/updated prognosis.
Daily deliberation for appropriate level of care	Routine daily discussions among members of the ICU treating team aimed at confirming that medical/surgical interventions administered to a patient are not disproportionate and/or do not contradict his/her preferences.
EOL discussions during family meetings	Conferences (on admission, and followed up at least as appropriate/feasible) of at least one member of an ICU patient's family and at least one member of the treating team aimed at determining and/or revising/adjusting EOL treatment goals according to the evolution of the patient's clinical course and (particularly changes) of prognosis, and "previously clarified" EOL values/preferences. This variable focuses on a specific type of family meetings' content aimed at achieving consistency between patient wishes and provided EOL care.
Written ICU triggers for limitations	A set of written, pre-specified medical and/or bioethical criteria for limiting LSTs in the ICU. Examples of such criteria may include: family request, presence of a pertinent living will that has to be respected, irreversible condition, un-survivable injury, severe brain injury with poor prognosis (e.g. minimally conscious state), high Sequential Organ Dysfunction Score plus poor response to acute illness treatment, multiple organ failure (≥ 3 organs), non-beneficial therapy, and terminal illness.
Written ICU EOL guidelines	Written ICU recommendations (e.g. shared decision making, or obligation to inform the family about poor patient response to treatment, and/or lack of expected benefit from available and/or ongoing LSTs), with a written expectation to be followed for EOL decision-making and application of EOL decisions.
Written ICU EOL (symptom management) protocols	A written set of ICU recommendations and standards aimed at preventing any kind of patient distress (e.g. pain, dyspnea, delirium) during the application of LST limitation decisions on withholding and/or withdrawing of LSTs; written ICU EOL protocols may be based on recent, pertinent recommendations on how to perform withdrawing of LSTs.
Palliative care consultations	Consultations and/or liaison with specialists from the hospital's (specifically designated) palliative care service, focused on the treatment of symptoms (e.g. dyspnea, pain, or delirium), rather than the treatment of any underlying disease processes. Psychosocial and spiritual needs may also be attended to in patients who do not require sedation and are able to communicate. Such consultations may take place whenever LST limitation is considered, in the context of communication of available treatment options to the patient/family. An exception to the former requirement pertains to the presence of an intensivist with palliative care expertise in the ICU treating team.
Ethics consultations	Consultations and/or liaison with a specialist from the hospital's (specifically designated) clinical ethics committee, focused on addressing of any ensuing ethical dilemmas and/or challenges, including disagreements (that cannot otherwise be resolved) between surrogate decision-makers, between the patient/family and the ICU treating team, health care professionals or others.

EOL Practice Variable	Definition
Communication courses	Lessons focused at developing or improving the capability of 1) expressing oneself clearly, honestly, and accurately (about available treatment options), and also in a way that is readily understood by the patient/family; and 2) providing psychological support, and showing empathy to the patient/family.
Bioethics courses	Lessons focused on improving the knowledge, understanding of the widely accepted four Principles of Bioethics, and/or the capability of effectively addressing ethical dilemmas and challenges of routine clinical practice.
Country EOL guidelines	Written recommendations by national medical societies, or statutory governing bodies, for EOL decision making and EOL practices (e.g. symptom control and/or procedure for withdrawal of mechanical ventilation) in the ICU.
Country EOL legislation	A set of laws aimed at addressing commonly ensuing ethical issues as part of routine clinical practice (e.g. Should advance directives always be followed? Are withholding or withdrawing of LSTs, or active shortening of the dying process legally allowed?, etc.).
EOL practice score	The sum of binary (i.e. 0 or 1) grading of the 12 EOL practice variables according to their absence (=0) or presence (=1); score range: 0-12.

25.1. Do you believe that there is adequate focus on palliative care needs in your ICU?

Yes, to a very high degree

Yes, to a high degree

Yes, to some degree

Yes, but to a low degree

No, not at all

Do not know

